1. AMENDMENT HISTORY

Amendment No.	Protocol Version No.	Date issued	Author(s) of changes	Details of Changes made

2. SYNOPSIS

Study Title	Assessment of the Occuity PM1 pachymeter
Research question / hypothesis	Is the Occuity pachymeter non inferior in it's measurement of central corneal thickness compared to the ultrasound pachymeter, Lenstar and Pentacam.
Study Design	Research Study
Study Participants	Volunteers with no corneal pathology
Planned Sample Size	82-100 participants
Follow-up duration	N/A
Planned Study Period	1 month
Primary Objective	To determine whether the Occuity PM1 device is non-inferior in measuring central corneal thickness when compared to ultrasound pachymetry, the Lenstar and the Pentacam.
Secondary Objectives	The Investigation aims to assess long-term safety of the Occuity PM1 device when used under the conditions and for the purposes intended, to ensure it will not compromise the clinical condition or the safety of patients, or the safety and health of users or, where applicable, other persons.
Primary Endpoint	The central corneal thickness measurements taken by the three devices: Occuity PM1, the ultrasound pachymeter and Lenstar. Demonstrating that the Occuity PM1 Pachymeter is not inferior to the LenStar in terms of equivalency to a 95% confidence level using the Bland Altmen equation/approach based on +/-20micron equivalency.
Secondary Endpoints	If evidence is not sufficient to demonstrate that the PM1 Pachymeter does not perform outside of the target range, it is understood that further investigation may be required. If it is deemed that further clinical investigation(s) are required, it is understood that a new MHRA application will be undertaken.
Safety Outcomes	The type and number of adverse events, serious adverse events and any other device issues will be recorded. Adverse events and devices issues not reflected on the product label will be reported to the manufacturer and, for the Occuity product, will be dispositioned according to the Sponsor's complaint handling procedures for post-market products.
Intervention (s)	N/A

3. BACKGROUND AND RATIONALE

The cornea is a thin, transparent structure at the front of the eye; its surface, as well as the overlying tear film, is responsible for the majority of the eye's refractive power.

Accurate and precise measurement of corneal thickness is important in the diagnosis and management of many ocular diseases. In particular, the central corneal thickness (CCT) measurement is a key parameter to consider when planning for procedures such as refractive surgery, and in the diagnosis of glaucoma.

Refractive error is the leading cause of reversible visual impairment worldwide; it is therefore unsurprising corrective refractive surgery is one of the most widely performed procedures globally. In the United Kingdom, the most frequently performed refractive surgery are laser assisted surgical procedures, such as laser assisted in situ keratomileusis (LASIK), Laser epithelial keratomileusis (LASEK), and Photorefractive Keratectomy (PRK). All of these techniques involve ablating the cornea with a laser to achieve a specific shape. Having an accurate measurement of corneal thickness is therefore of utmost importance in the planning stages, as excessive ablation of the cornea can lead to corneal ectasia, a significant complication of refractive surgery.

Glaucoma is a progressive disease which causes irreversible vision loss, and with ever aging populations, it is now one of the leading causes of irreversible blindness worldwide. Although it is considered to be multifactorial in aetiology, with both genetic and acquired factors contributing to its development and progressions, it is still widely accepted that the intraocular pressure (IOP) is the only modifiable factor in its management to prevent or slow further visual loss. (5).

IOP measurement is typically done in hospital clinics using a Goldmann applanation tonometer. The pressure reading is affected by the corneal thickness – a thick cornea will give a falsely elevated IOP reading, which may result in a patient with healthy eyes being commenced on unnecessary treatment, while conversely a thin cornea may give a falsely low pressure reading, which can result in patients with glaucoma not being started on sight-saving treatment. It has been estimated that a 10% increase in CCT can result in an apparent IOP increase of 3.4mmHg (2).

Ultrasound Pachymeter

The ultrasound pachymeter (UP) is currently the gold standard method, as well as the most widely used to measure CCT. In comparative device studies, the ultrasound pachymeter has been shown to provide the most repeatable measurements. In addition, it is a small and portable handheld device, which makes it very convenient and timesaving to use during clinic appointments.

However, there are several negative aspects to the UP. First, it is necessary for the device to make direct contact with the cornea, which introduces the risk of corneal abrasions and subsequent infection. Second, anaesthetic eye drops need to be used for the patients to tolerate the corneal touch, and studies have shown that after instillation of anaesthetic eye drops, the CCT measurement is increased compared to before the use of anaesthetic, which can lead to a systematic over-reading of IOP. Third, the UP can be difficult to use, as it is necessary for the probe to contact the cornea perpendicularly, and exactly at the centre of the cornea to achieve the most accurate reading, which is difficult to achieve even with good staff training and experience. Lastly, despite the use of anaesthetic, measurement using this device

is uncomfortable, and sometimes poorly tolerated due to the corneal touch, especially by the paediatric population.

While there are optical devices available on the market which can measure CCT without the instillation of anaesthetic or corneal touch, they tend to be bulky machines which are not portable and require specialist training to use. This makes their use in busy hospital clinics and community optometry practices less feasible.

There is a clear need to develop a device which can measure CCT accurately without necessitating corneal touch and use of topical anaesthetic, as well as being easily portable. There is no such device available on the market currently, and in our search in the clinical trial databases and we did not identify any active trials investigating similar devices.

Occuity PM1 Pachymeter

The Occuity device is a new handheld, non-contact, optical pachymeter, which utilise a low power, eye safe near infrared (1310nm) beam to measure the corneal thickness.

The device has an intuitive touchscreen display interface, and a series of 9 LEDs which provides the illumination needed to align the device in front of the eye. Once alignment is achieved, the measurement can take place by pressing the start button on the touchscreen display. During preliminary testing at the parent company, it has been shown the alignment and measurement process takes less than 10 seconds in total, after which a reading will be shown on the digital display of the device. The device is reported to have high reliability (variation of approximately 10um with repeat readings of the same eye), and comparable results to the Lenstar LS900 Biometer during initial testing.

The LED light system consist of a partial ring of 9 white LEDs at a radius of 8.75mm and spaced at 30° intervals. The total power is 2.4 mWm⁻² which is will within the 10 mWm⁻² blue light hazard eye safety limit. The maximum power of the infrared beam is 50µW, which given the expected exposure time of less than 10 seconds, is considered Class 1 eye safe according to BS EN 60825.

Lenstar LS 900 (Haag-Streit AG, Koeniz, Switzerland)

The Lenstar is an optical device which utilises an 820nm super-luminescent diode and allows for high resolution measurements of the structures in the eye, including CCT. Its use is well established in the hospital clinic setting, and measurements do not require the use of anaesthetic drops or corneal touch. A drawback of this device is that it is large and heavy, and therefore not portable or as fast to use, unlike the ultrasound pachymeter or the Occuity PM1 device.

Pentacam (Oculus Optikgerate GmbH (Germany)

Very similar to the Lenstar, the Pentacam is an optical device which also utilises an 820nm super-luminescent diode and allows for high resolution measurements of the structures in the eye, including CCT. Its use is well established in the hospital clinic setting, and measurements do not require the use of anaesthetic drops or corneal touch. A drawback of

this device is that it is large and heavy, and therefore not portable or as fast to use, unlike the ultrasound pachymeter or the Occuity PM1 device.

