4. AIMS AND OBJECTIVES

Primary Objective

To determine whether the Occuity PM1 device is non-inferior in measuring central corneal thickness when compared to ultrasound pachymetry, the Lenstar and the Pentacam.

Secondary Objective

The Investigation aims to assess long-term safety of the Occuity PM1 device when used under the conditions and for the purposes intended, to ensure it will not compromise the clinical condition or the safety of patients, or the safety and health of users or, where applicable, other persons.

If the evidence collected during this investigation is not sufficient to demonstrate that the PM1 Pachymeter does not perform under the conditions and for the purposes intended, it may be deemed possible that further investigation may be required. If it is deemed that further clinical investigation(s) are required, it is understood that a new MHRA application will be undertaken.

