5. STUDY DESIGN

6.1 Summary of Study Design

This is a prospective, observational, non-invasive, crossover study. The participants will undergo CCT measurement using the Occuity PM1 device, Lenstar device, the Pentacam and then the Ultrasound pachymeter, which is standard of care. Measurement with ultrasound will occur last, as this will require instillation of anaesthetic drops which may confound the values obtained by the Occuity and other devices.

The participants will be recruited and will be measured by City University Clinicians. No additional visits will be required. The measurements will take place during their clinic appointment and will take approximately 30 minutes to complete.

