8. STUDY PROCEDURES

Only 1 study visit will be required.

The following procedures will be undertaken for the study, in time order:

1. Investigator to explain the study to patient, provide PIS, and obtain informed consent
2. CCT measurement using Occuity device
3. CCT measurement using Pentacam device
4. CCT measurement using Lenstar device
5. Instillation of Minims Proxymetacaine Hydrochloride 0.5% eye drops to the study eye
6. CCT measurement using Ultrasound Pachymeter

The devices will need cleaning between patients.

- The PM1 is to be cleaned with 70% isopropyl alcohol wipes to prevent patient-to-patient infection.
- The Lenstar device is to be cleaned with 70% isopropyl alcohol wipes will have the paper chin rest strip replaced.
- The Pentacam device is to be cleaned with 70% isopropyl alcohol wipes will have the paper chin rest strip replaced.
- The ultrasound probe will be wiped with a Q-tip soaked in 70% isopropyl alcohol. The tip will then be rinsed in sterile distilled water before use.

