11. RANDOMISATION

The volunteers will be randomised *a priori* into one of two sequences – those in Sequence 1 who follow the sequence Lenstar, Pentacam, PM1 then ultrasound and Sequence 2 who will follow the sequence Pentacam, PM1, Lenstar, ultrasound. The order in which subjects will be allocated to each sequence will be generated by a validated software prior to the start of the study to allocate the volunteers to each sequence.

NOTE: Ultrasound cannot be included within the randomisation as the anaesthesia required to undertake the US methodology would result in the Occuity PM1 & Lenstar measurements being unable to be recorded.

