17.2 Analysis of Endpoints

On completion of data collection, the primary endpoint will be analysed using paired tests or non-parametric equivalents, to compare the CCT measurement achieved using the ultrasound pachymeter and the Occuity PM1 device, and then between the values obtained from the Lenstar, Pentacam and Occuity PM1 device. The level of statistical significance will be set at $p < 0.05$.

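### Ultrasound is always read last and after anaesthetic drops, so the PM1–ultrasound comparison cannot separate a device difference from the drop and order effect

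*Protocol*

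**What the plan says.** Section 3 (Background and Rationale, under Ultrasound Pachymeter) reports that, once drops are in, "the CCT measurement is increased compared to before the use of anaesthetic". It lists this among the drawbacks of ultrasound and gives no size for the effect.

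Section 6.1 fixes the order: "Measurement with ultrasound will occur last, as this will require instillation of anaesthetic drops which may confound the values" from the other devices. In Section 8 the step directly before ultrasound is "Instillation of Minims Proxymetacaine Hydrochloride 0.5% eye drops to the study eye", and Section 12 repeats this. Section 11 states "Ultrasound cannot be included within the randomisation" and puts ultrasound last in both sequences. Sections 8 and 12 give a different order of the optical devices from Section 11, but ultrasound is last, after drops, in all of them. No optical reading is planned after the drops and no ultrasound reading before them.

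The primary objective (Synopsis and Section 4) is to show the PM1 to be "non-inferior in measuring central corneal thickness when compared to ultrasound pachymetry, the Lenstar and the Pentacam". Section 17.2 plans paired tests or non-parametric equivalents at p < 0.05, first "to compare the CCT measurement achieved using the ultrasound pachymeter and the Occuity PM1 device", then among the optical devices.

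Two further statements matter. The Synopsis and Section 6.2 give one explicit success criterion: PM1 against Lenstar, within ±20 µm. Section 7 (Sampling) uses a limit of 2 µm, names no comparator and arrives at 163 eyes.

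**The concern.** The fixed order protects the optical readings from the drops. It does nothing for the contrast between PM1 and ultrasound, where one reading is always before drops and the other always after. By the protocol's own account the drops push the second reading up. Device, drop and last-position effects are thus completely aliased in that contrast, and no analysis of the planned data can pull them apart.

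The contrast is nevertheless part of the primary objective and is named first in the primary analysis. A PM1 that is exactly right on the undropped cornea would appear to under-read. A PM1 that over-reads by about the drop effect would appear to agree. A significant paired test could then be charged to the PM1 when it reflects the drops, and a non-significant one could be credited to it when it should not be.

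**Working it through.** **1. What each contrast estimates.** Let *m* be the true pre-drop thickness, δ the systematic error of each device, and *b* the upward shift from drops together with any last-position effect.

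- PM1 − Lenstar = δ(PM1) − δ(Lenstar). No *b*.
- PM1 − Pentacam = δ(PM1) − δ(Pentacam). No *b*.
- PM1 − ultrasound = δ(PM1) − δ(ultrasound) − *b*.
- Lenstar − ultrasound = δ(Lenstar) − δ(ultrasound) − *b*, and likewise for Pentacam.

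Every contrast that contains *b* also contains δ(ultrasound), so *b* cannot be estimated on its own.

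**2. The plan's own figure.** Section 7 gives n = f(α, β) × 2 × σ² / d², with α 0.025 (taken as one-sided), power 0.95 and d = 2 µm. f = (1.960 + 1.645)² = 12.995. No σ is given. Back-solving, σ = √(163 × 4 / (2 × 12.995)) = 5.01. With σ = 5, n = 12.995 × 2 × 25 / 4 = 162.4, rounded up to 163. With σ = 4.5 the answer is 132, and with 5.5 it is 197. So 5 µm fits, but it is inferred from the result. The 95% baseline below is therefore built in and is not independent evidence.

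**3. Effect of the shift at the 2 µm limit.** SE = 5 × √(2/163) = 0.554 µm, treating the 163 eyes as independent. With no true device difference and the limit on the side toward which the shift moves, power = Φ((2 − *b*)/0.554 − 1.96). If the PM1 truly over-reads by 2 µm and an upper limit of 2 µm applies, the chance of a false pass = Φ(*b*/0.554 − 1.96). The size of *b* is assumed throughout.

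| Assumed *b* (µm) | Power, no device difference | Eyes for 95% power | False pass, true over-reading of 2 µm |
|---|---|---|---|
| 0 | 95% | 163 | 2.5% |
| 0.5 | 77% | 289 | 14.5% |
| 1 | 44% | 650 | 44% |
| 1.5 | 14.5% | 2599 | 77% |
| 2 | 2.5% | unattainable | 95% |

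If the only limit lay on the other side, the shift would raise the pass rate, as in the last column.

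**4. The planned paired test.** It has no margin. With no device difference and *b* = 2 µm, it is significant with probability Φ(2/0.554 − 1.96) = 95%, from the drop effect alone.

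**5. Effect of the shift at ±20 µm.**

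- *Mean difference.* Even at *b* = 10, (20 − 10)/0.554 − 1.96 = 16.1, so power stays at about 100%.
- *Limits of agreement.* The SD of differences is 5 × √2 = 7.07, so the limits are −*b* ± 1.96 × 7.07 = −*b* ± 13.86. At *b* = 5 they are −18.9 to +8.9. The lower limit reaches −20 at *b* = 20 − 13.86 = 6.14. At *b* = 10 they are −23.9 to +3.9.
- *Sensitivity.* If the SD of differences were 10, the limits would be ±19.6 with no shift at all, and *b* = 0.4 would reach −20.

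**The case against.** The strongest reply is that drops belong to ultrasound pachymetry. Section 3 says they are needed for patients to tolerate the probe, and describes ultrasound as the gold standard and most widely used method. Section 6.1 calls it standard of care. Agreement between the PM1 and ultrasound as actually practised is a meaningful quantity, and the drop effect is then part of the reference method. This stands. What the protocol lacks is a statement that this is the target. Its rationale leans the other way, since it treats the drop-induced rise as a fault that a no-anaesthetic device would avoid.

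Second, the only explicit success rule is against Lenstar, measured before drops. This also stands: that criterion and the Pentacam comparison are untouched.

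Third, the large power losses depend on the 2 µm limit, an inferred SD and an assumed shift, whereas the endpoint margin is ±20 µm. This too stands, and the figures should be read as sensitivity only. But the protocol ties ±20 µm to Lenstar and assigns no margin to ultrasound, so the lenient case cannot simply be presumed.

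Fourth, limits on interpretation could sit in an analysis plan that is not shown. That is fair for labelling. The objective, the order and the test, however, are all fixed in the protocol.

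**Conclusion.** The point holds as a limit on interpretation. The PM1–ultrasound difference mixes device, drop and order effects, and the design offers no way to separate them. The bias can run against the PM1 or in its favour.

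A reader might infer that the ultrasound comparison cannot support any non-inferiority claim, or that the trial's primary conclusion fails. The documents do not support that. A claim limited to agreement with post-anaesthetic ultrasound is interpretable, and the stated Lenstar criterion does not involve the drops.

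The size is unknown because the protocol gives neither the drop effect nor the SD. With an SD of 5 µm, 163 independent eyes and a limit on the side of the shift, 1 µm is enough to cut power from 95% to 44% at the 2 µm limit. At ±20 µm the mean difference is barely affected up to a 10 µm shift. Limits of agreement are breached only above about 6 µm, or sooner if the SD of differences exceeds 7.07 µm. How much this matters therefore turns largely on which margin applies.

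**What to change.** - In the Synopsis, Section 4 and Section 17.2, state that the ultrasound conclusion concerns agreement with post-anaesthetic ultrasound as used in practice, not device performance on the same corneal state.
- Base the confirmatory claim on the pre-drop Lenstar criterion that the Synopsis and Section 6.2 already contain.
- Say in Section 17.2 that a significant PM1–ultrasound paired test will not be read as PM1 error.
- Report Lenstar–ultrasound and Pentacam–ultrasound differences in the same eyes beside it. They are context and not a correction, because each carries its own device difference.
- Reconcile the 2 µm limit in Section 7 with the ±20 µm in Section 6.2, and say which comparison each serves.

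The cost is a narrower claim against ultrasound, revised wording and two extra descriptive contrasts from data already collected. Ultrasound can stay in the objective on these terms. Removing the protocol's own gold standard altogether would change the research question and is a debatable trade-off. No procedure changes.

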4. AIMS AND OBJECTIVES

Primary Objective

To determine whether the Occuity PM1 device is non-inferior in measuring central corneal thickness when compared to ultrasound pachymetry, the Lenstar and the Pentacam.

Secondary Objective

The Investigation aims to assess long-term safety of the Occuity PM1 device when used under the conditions and for the purposes intended, to ensure it will not compromise the clinical condition or the safety of patients, or the safety and health of users or, where applicable, other persons.

If the evidence collected during this investigation is not sufficient to demonstrate that the PM1 Pachymeter does not perform under the conditions and for the purposes intended, it may be deemed possible that further investigation may be required. If it is deemed that further clinical investigation(s) are required, it is understood that a new MHRA application will be undertaken.

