14. DEFINITION OF END OF STUDY

The end of study is the date of the last assessment of the last participant.

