15.5 Definitions

A serious adverse event is any untoward medical occurrence that:

- Results in death,
- Is life-threatening,
- Significant decline in vision (Defined as irreversible loss of 10 EDTR letters)
- Requires inpatient hospitalisation or prolongation of existing hospitalisation,
- Results in persistent or significant disability/incapacity, or
- Is a congenital anomaly/birth defect.
- Other important medical events*

*Other events that may not result in death, are not life threatening, or do not require hospitalisation, may be considered a serious adverse event when, based upon appropriate medical judgement, the event may jeopardise the participant and may require medical or surgical intervention to prevent one of the outcomes listed above.

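### The secondary objective is long-term safety, but the protocol plans a single visit and no observation after it, so the objective should be narrowed or matched with follow-up

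*Protocol*

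**What the plan says.** Section 4 of the protocol has one secondary objective: "The Investigation aims to assess long-term safety of the Occuity PM1 device". The Synopsis repeats it in the same terms.

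The design is described as follows:

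- Synopsis: the row "Follow-up duration" is N/A, and the row "Planned Study Period" is 1 month for the whole study.
- Section 6.1: "No additional visits will be required", and the measurements "will take approximately 30 minutes to complete".
- Section 8: "Only 1 study visit will be required".
- Section 14: "The end of study is the date of the last assessment of the last participant".

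On safety data, Section 6.2 has adverse events, serious adverse events and device issues recorded by type and number, and Section 15.7 requires a report form for each adverse event. Section 13 arranges follow-up of serious or device-related events until they resolve, stabilise or are given a cause unrelated to the study.

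**The concern.** The objective names a time horizon that the schedule does not contain. Each participant is seen once, no later contact is planned, and the study closes with the last measurement. An effect that begins after a participant has left would come to light only if the participant happened to report it.

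What is at stake is the safety claim. This is the only secondary objective. If the text stands, a study in which nothing untoward happens at the visit could be reported as having met a long-term safety objective, although nothing was planned that could have shown the opposite.

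**Working it through.** No figure in the protocol needs reproducing here; the sample size in Section 7 concerns corneal thickness and has no bearing on this point. The check compares what the objective requires with what each section supplies.

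**1. Planned contacts after the measurement visit.** Section 8 gives one visit in total and Section 6.1 no additional ones: 1 − 1 = 0 later contacts.

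**2. Planned follow-up time.** The Synopsis entry is N/A. No other section gives a telephone call, questionnaire or return visit for participants without an identified event.

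**3. Length of the visit.** Section 6.1 gives about 30 minutes for the measurements. Consent and a short history (Sections 10 and 12) come on top, so 30 minutes is not the whole visit, but it remains a single attendance. Section 15.1 expects less than 10 seconds of infrared exposure from the PM1.

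**4. Longest interval the study could cover.** If the 1-month study period runs from the first visit to the last assessment (an assumption; the protocol does not say), the first participant has at most about 1 month between visit and end of study. The last participant has none, because Section 14 ends the study at that person's last assessment. No one is contacted in the interval.

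**5. Does a safety endpoint fill the gap?** The safety outcome in Section 6.2 counts events and sets no post-visit window or contact. The text headed as the secondary endpoint, in the Synopsis and Section 6.2, says when further investigation and a new regulatory application may be needed. It is not a safety measure.

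**6. Does Section 13 fill it?** It starts from an event already identified. It can show how that event turned out. It cannot find delayed events among participants who left without one, and so it cannot give a long-term frequency.

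The data collection thus supports a statement about safety around the visit, plus the course of any identified event. It does not support the objective's time horizon.

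**The case against.** The strongest defence is that the protocol does attend to safety. Events and device issues are recorded, each adverse event has a form, serious and device-related events are followed to an outcome, and PM1 issues enter the sponsor's complaint handling. This stands. A reader might infer that the study collects no safety data at all; Sections 6.2, 13 and 15.7 show otherwise. The fault is the time horizon.

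It can also be said that Section 4 already allows for insufficient evidence and further investigation. That wording is conditional on what the study finds. For long-term safety the shortfall is known before the first participant is enrolled.

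A separate analysis plan may exist, but it could not help here: the objective, the visit schedule and the end of study are all fixed in the protocol, and an analysis plan cannot supply observations that are not made.

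Two further readings are tempting, and the document does not support them:

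- Section 15.5 lists a decline in vision, "Defined as irreversible loss of 10 EDTR letters", among the criteria for a serious event. A reader might infer that an acuity endpoint is promised and left unmeasured. The criterion only classifies events that arise, and Section 13 offers a way to establish irreversibility in an identified case.
- A reader might infer that no same-visit event can be attributed to the PM1, because anaesthetic drops and contact ultrasound are given at the same visit. They come last in every order stated (Sections 6.1, 8, 11 and 12), so an event seen before them cannot be due to them. Attribution of later events is a separate matter and would remain whatever the objective is called.

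**Conclusion.** The inconsistency is real and can be read directly from the protocol: a long-term objective is set beside a design with zero planned observation after one visit. The study can describe safety around that visit; it cannot support a long-term conclusion.

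The weight is moderate. The primary comparison, its margin, the sample size and the participant procedures are untouched. The only assumption is that no follow-up is planned beyond what the protocol describes, which the N/A entry in the Synopsis supports.

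A reader might want to express the size as an upper confidence bound for zero events in 82 to 100 participants. Such a bound would hold for same-visit events in any study of that size, whatever its objective, and does not measure this mismatch. The relevant figure is the zero.

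**What to change.** Reconcile the Synopsis and Section 4 with Sections 6.1, 8 and 14. There are two ways:

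1. **Narrow the objective.** In the Synopsis and Section 4, replace long-term safety with safety during the single study visit, including follow-up of identified serious or device-related events under Section 13. Add a sentence that the study does not assess long-term or delayed effects. Section 15.5 can stay as it is, since it classifies events. This costs two wording changes and one added sentence, with no new procedures. The downside is a narrower safety claim.
2. **Keep the objective.** The sponsor then has to define a follow-up period and a safety endpoint that match it, and revise the follow-up entry, the visit statements and the end-of-study definition accordingly. This costs additional participant contact and probably a longer study.

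The choice is the sponsor's. The first route is enough to remove the contradiction.
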